8.5. Secondary Analyses

The proportion of subjects with HCV RNA below the LLoQ over time (including SVR endpoints) will be presented by treatment arm in tabular and graphical form.

8.6. Safety Analysis

Safety will be evaluated by assessment of clinical laboratory tests, physical examinations, vital signs measurements, at various time points during the study, and by the documentation of AEs. All safety data collected while "on treatment" (i.e., on or after the first dose of study drug administration up to 30 days after the last dose of study drug) will be summarized by treatment arm according to the study drug received.

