Subjects in the advanced lung disease cohort must have been diagnosed with chronic obstructive pulmonary disease (COPD) or interstitial lung disease (ILD) must meet **ALL** HCV criteria, and meet the following criteria for COPD or ILD:

- ILD criteria: diagnosis of interstitial lung disease with chronic supplemental oxygen requirement at rest and/or with exertion.
- COPD criteria (one of the following):
 - Forced expiratory volume (FEV1)< 30% predicted
 - OR any FEV1 with chronic supplemental oxygen requirement at rest and/or with exertion
 - OR any FEV1 with chronic hypercapnea (baseline partial pressure of arterial carbon dioxide [PaCO2] > 45)

Subjects may not present with any of the criteria:

- Genotype 2 or 3 infection
- Treatment with any of the following agents
 - Amiodarone. Subjects previously treated with amiodarone must have stopped the amiodarone at least 60 days prior to day 1 of SOF/LDV FDC
 - Carbamazepine, phenytoin, phenobarbital, oxcarbazepine
 - o Rifabutin, rifampin or rifapentine
 - HIV regimens containing tenofovir or tipranavir/ritonavir
 - o St. John's wort
 - Rosuvastatin
- Have any serious or active medical or psychiatric illness which, in the opinion of the investigator, would interfere with subject treatment, assessment, or compliance
- History of hepatic encephalopathy or variceal hemorrhage
- Hepatitis B surface antigen positive
- Abnormal hematological and biochemical parameters, including:
 - Hemoglobin (Hb) < 8 g/dL

- Platelets \leq 50,000/mm³
- ALT (alanine aminotransferase), AST (aspartase aminotransferase), or alkaline phosphatase ≥ 10 times ULN
- Total bilirubin > 3 mg/dl
- Severe renal impairment creatinine clearance (CrCl), i.e. < 30 mL/min.
- History of major organ transplantation with an existing functional graft.
- History of clinically-significant drug allergy to nucleoside/nucleotide analogs.
- Pregnant women or women planning to become pregnant
- Women who are breastfeeding
- Active or recent history (≤ 1 year) of drug or alcohol abuse

Study Procedures/ Frequency:

Study visits will occur at screening, baseline/day 1, weeks 2, 4, 8, 12 for the 12-week treatment group and also weeks 16, 20 and 24 for the 24-week treatment group. Post-treatment follow-up visits will be performed at 4 and 12 weeks following the last dose of study drug for both groups.

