Screening assessments include physical examination with height and weight measurements, vital signs, medical history review for eligibility determination, safety laboratory tests, HCV RNA and HCV genotyping, HIV and HBV testing, serum β-hCG (females of childbearing potential only), ECG, and Fibroscan (if needed)

On-treatment assessments include adverse events (AEs) assessments, concomitant medications, physical examination, vital signs, safety laboratory tests, HCV RNA, ECG

Post-treatment assessments include adverse events (AEs) assessments, concomitant medications, physical examination, vital signs, safety laboratory tests, HCV RNA, ECG

Test Product, Dose, and Mode of Administration:

All study subjects will receive the sofosbuvir 400 mg and ledipasvir 90 mg fixed dose combination. Subjects will take one tablet in the morning.

Evaluation criteria Safety

AEs that lead to discontinuation, SAEs and safety laboratory tests will be collected until 4 weeks after the last dose of study drug. Safety endpoints will include

- Completion of full course of therapy
- Discontinuation for adverse events
- Serious adverse events

Efficacy

Efficacy will be evaluated using scheduled assessments of HCV RNA by PCR. All endpoints will be summarized with descriptive

statistics by cohort. Number and percent of subjects in each cohort will be presented for categorical variables. For continuous variables, N, mean, SD, Median, Q1, Q3, minimum and maximum will be presented.

The primary efficacy endpoint will be the SVR12 defined as HCV RNA < LLoQ for 12 weeks post-treatment.

GLOSSARY OF ABBREVIATIONS AND DEFINITION OF TERMS

AE adverse event

ALT alanine aminotransferase AST aspartate aminotransferase

BMI body mass index
BW Body weight
CLcr creatinine clearance

COPD Chronic obstructive pulmonary disease

CRF case report form(s)

dL deciliter

ECG electrocardiogram
e.g. For example
ET Early termination

FDA (United States) Food and Drug Administration

FDC Fix Dosed Combination FEV1 Forced expiratory volume

GCP Good Clinical Practice (Guidelines)

Hb hemoglobin

hCG human chorionic gonadotropin

HBV Hepatitis B virus HCV Hepatitis C virus

HIV Human Immunodeficiency Virus

ICF Informed Consent Form

ICH International Conference on Harmonisation

i.e. for explanation

ILD Interstitial lung disease
INR International normalized ratio
IRB institutional review board

LDV ledipasvir

LLoQ lower limit of Quantification MCV Mean corpuscular volume

mg milligram
mL milliliter

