3. SUBJECT POPULATION

3.1. Treatment plan and regimen

Approximately 25 subjects with chronic HCV and advanced heart failure; and 25 subjects with chronic HCV and advanced lung disease will be enrolled. Subjects must have genotype 1, 4, 5 or 6 HCV. All subjects will receive SOF/LDV FDC. The duration of treatment will be 12 weeks for treatment naïve subjects with or without cirrhosis. All subjects will receive 12 weeks of the SOF/LDV FDC except for treatment experienced genotype 1 subjects with cirrhosis, who will receive 24 weeks of treatment. All subjects will continue in the study follow-up period for 12 weeks after treatment has been completed.

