5.2.7. Post-Treatment Weeks 4 and 12 (± 5 days)

- Obtain vital signs (includes resting blood pressure, pulse, respiratory rate and temperature)
- Assessment of AEs and concomitant medications
- Obtain blood samples for:
 - Hematology
 - Chemistry
 - HCV RNA
- Urine β-hCG pregnancy test (females of child bearing potential only).
- ECG

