8.6.1. Adverse Events

Clinical and laboratory adverse events will be summarized on the basis of the date of onset for the event. A treatment-emergent adverse event will be defined as any adverse event that begins on or after the date of first dose of medicinal product up to the date of last dose of medicinal product plus 30 days.

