APPENDIX 1. STUDY PROCEDURES TABLE

Procedure	Screening: Day -28 to -1	Baseline Day 1 ¹	Week 2	Week 4	Week 8	Week 12	Week 16	Week 20	Week 24	Early Term or Unscheduled	Post- treatment Week 4	Post- treatment Week 12
Informed Consent	Х											
Eligibility review ²	Х	Х										
AE and con meds assessment		X	Х	Х	Х	Х	Х	Х	Х	Х	Х	Х
Pregnancy prevention counseling		X										
Dispense and instruct on use of drug		X										
Medication Compliance			Х	Х	Х	Х	Х	Х	Х	X		
Medical History	Х											
Physical exam ³	X	X								X		
Vital signs ⁴	X	Х	Х	Х	Х	Х	Х	Х	Х	X	Х	Х
Weight ⁵	X	X				Х			Х	X		

¹ All physical procedures and review procedures to be performed prior to dispensing or dosing with drug

² Includes adequate documentation of start/stop dates for prior HCV therapy; prior viral response data; and chronic HCV infection. Includes review of excluded concomitant medications.

³ General appearance; body system review: head, neck, thyroid, eyes, ears, nose, throat, mouth and tongue; chest (excluding breasts); respiratory, cardiovascular; lymph nodes, abdomen; skin, hair nails; musculoskeletal; neurological

⁴ Resting blood pressure, pulse, respiratory rate, and temperature

⁵ Weight to be obtained at last treatment visit, either week 12 or week 24

Procedure	Screening: Day -28 to -1	Baseline Day 1 ¹	Week 2	Week 4	Week 8	Week 12	Week 16	Week 20	Week 24	Early Term or Unscheduled	Post- treatment Week 4	Post- treatment Week 12
Height	Х											
ECG ⁶	X			Х		Х			Х	X	X	Х
Fibroscan ⁷	Х											
Laboratory Assessmen	nts											
Hematology ⁸	X	X	Х	Х	Х	Х	Х	Х	Х	Х	Х	Х
Chemistry ⁹	Х	Х	Х	Х	Х	Х	Х	Х	Х	X	Х	Х
Coagulation ¹⁰	X					Х			Х	X		
HCV RNA	Х	X	Х	Х	X	Х	Х	Х	Х	X	X	Х
HCV Genotype	Х											
HIV serology	X											
HBV serology	X											
Serum β-hCG	Х											
Urine β-hCG ¹¹		Х	Х	Х	X	Х	Х	Х	Х	X	Х	X

⁶ After resting in supine position for \geq 5 minutes

⁷ If not done within 6 months of screening

⁸ Includes hematocrit, hemoglobin (Hb), platelet count, red blood cell count (RBC), white blood cell count (WBC) with differential (absolute and percentage) including lymphocytes, monocytes, neutrophils, eosinophils, basophils, reticulocyte count and MCV

⁹ Alanine aminotransferase (ALT/SGPT), Aspartate aminotransferase (AST/SCOT), albumin, alkaline phosphatase, serum creatinine, total bilirubin (direct bilirubin as reflex if total is elevated), glucose, lipase, potassium, and sodium

¹⁰ Includes INR, and Prothrombin time (PT)

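### The synopsis ends safety data collection 4 weeks after the last dose, short of the 30-day analysis window and of the Week 12 labs, and no section says whether SAEs starting after day 30 are entered or reported

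*Combined protocol and SAP*

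**What the plan says.** **Collection.** The Protocol Synopsis, under the safety evaluation criteria, states: "AEs that lead to discontinuation, SAEs and safety laboratory tests will be collected until 4 weeks after the last dose of study drug".

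**Analysis.** Section 8.6 summarises as on-treatment the safety data collected "on or after the first dose of study drug administration up to 30 days after the last dose of study drug". Section 8.6.1 defines a treatment-emergent event as one that begins from the first dose "up to the date of last dose of medicinal product plus 30 days". Section 8.1.4 names the rate of SAEs as a safety endpoint and gives no window of its own. Section 8.6.2 summarises laboratory data by study visit, with no day limit.

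**Visits.** Section 3.1 states: "All subjects will continue in the study follow-up period for 12 weeks after treatment has been completed". Section 5.2.7 and Appendix 1 place AE assessment, hematology and chemistry at both post-treatment Week 4 and post-treatment Week 12, each with a margin of 5 days either way. The synopsis agrees on the visits ("Post-treatment follow-up visits will be performed at 4 and 12 weeks following the last dose of study drug for both groups") and on their content ("Post-treatment assessments include adverse events (AEs) assessments, concomitant medications, physical examination, vital signs, safety laboratory tests, HCV RNA, ECG").

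**Data entry.** Section 7.1 restricts database entry to AEs that lead to drug discontinuation or withdrawal. Section 7.2 has the investigator assess every AE but record on the AE page of the CRF only those that lead to discontinuation.

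**The concern.** Collection should last at least as long as the period being analysed, and should cover whatever the schedule requires sites to measure. Read literally, the synopsis does neither. It closes collection before the 30-day window ends, and it closes collection of labs before the Week 12 samples are drawn.

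A second gap lies behind this one. Sites assess AEs at Week 12, but nothing tells them whether an SAE found there is to be entered, and nothing tells the analyst whether to report it. Sites could handle such events differently.

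This matters because safety and tolerability are the primary objective and SAEs are a named safety endpoint. Late events are plausible: Section 3.4 requires every heart failure subject to have been hospitalized for heart failure in the 12 months before entry, and Section 7.3 lists in-patient hospitalization among the outcomes that make an event serious.

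**Working it through.** The plan gives no figure that depends on these windows, so there is none to reproduce. The check compares the periods.

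**Inputs**, in days after the last dose unless stated:
- end of collection, synopsis: 4 weeks = 28
- end of analysis window, 8.6 and 8.6.1: 30
- post-treatment Week 4 visit, 5.2.7: 28 ± 5 = 23 to 33
- post-treatment Week 12 visit, 5.2.7: 84 ± 5 = 79 to 89
- length of treatment, 3.1: 84 days, or 168 days for the 24-week group
- cohort size, 3.3: about 25 each

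**1. Collection against the analysis window.** The shortfall is 30 − 28 = 2 days. Measured from the first dose:

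| Course | To end of collection | To end of analysis window | Difference |
|---|---|---|---|
| 12 weeks | 84 + 28 = 112 | 84 + 30 = 114 | 114/112 − 1 = 1.8% |
| 24 weeks | 168 + 28 = 196 | 168 + 30 = 198 | 198/196 − 1 = 1.0% |

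The synopsis does not tie its 4 weeks to the Week 4 visit. If it were read that way, a visit on day d would leave max(0, 30 − d) days uncovered: 7 days for a visit on day 23, 1 day for day 29, and none from day 30 on. That is above zero on 7 of the 11 permitted days, so this reading does not reliably close the gap.

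**2. Collection against the lab schedule.** The Week 12 hematology and chemistry samples fall 84 − 28 = 56 days after the synopsis ends lab collection (79 − 28 = 51 to 89 − 28 = 61). This conflict is direct: the tests are scheduled, Section 8.6.2 would summarise them by visit, and the synopsis says collection has stopped.

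**3. SAEs after day 30.** From the end of the analysis window to the Week 12 visit is 84 − 30 = 54 days (79 − 30 = 49 to 89 − 30 = 59). AEs are assessed at the end of that period, but no section states what becomes of an SAE that began in it.

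**4. Entry rule.** An event that starts after the last dose cannot cause the drug to be stopped. Under 7.1 and 7.2 it would therefore not be entered, unless it leads to withdrawal and that word in 7.1 is read as withdrawal from the study. This applies to days 1 to 30 after the last dose as well as later, so lengthening the collection period in the synopsis would not be enough.

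**5. Scale.** With full follow-up (an assumption), one cohort contributes 25 × 54 / 365.25 = 3.7 patient-years between day 31 and nominal Week 12. The documents give no event rate. At assumed rates of 0.25 to 1 admission per subject-year this would be 3.70 × 0.25 = 0.9 to 3.70 × 1 = 3.7 admissions. These are counts of admissions, not of subjects with a first SAE.

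**The case against.** The strongest reply is that the plan does fix its analysis window. Sections 8.6 and 8.6.1 agree on 30 days, and an endpoint list in 8.1.4 that is silent on timing does not contradict the section that supplies it. This stands. A reader might combine 8.1.4 with the visit schedule and infer a third SAE period running to Week 12: 84 + 84 = 168 days, 50% longer than 112, or 168 + 84 = 252 days, 29% longer than 196. No passage states such a period, so that spread is not a property of the plan.

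A reader might also infer that events on days 29 and 30 are counted but necessarily lost. That holds only if the synopsis overrides Section 5.2.7. An AE assessment at a later visit can still identify such an event by its onset date.

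Third, assessing is not recording. Section 7.2 separates the two, so an AE assessment at Week 12 does not in itself contradict a shorter collection period. This also stands, and it leaves the labs as the only direct conflict with the visit schedule.

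Fourth, late events do not vanish. Section 9.1.6 requires source records of all AEs, and Section 7.3.1 has the investigator send the coordinating center a copy of the report to the regulator on any event judged related and unexpected. But source records do not tell a site what to enter, and the reporting route covers only that subset.

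Finally, the lead-in to the SAE definition in 7.3 refers to an adverse drug experience, which leaves open whether every admission for the underlying disease qualifies. That is a further reason not to put a number on the late events.

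**Conclusion.** The point holds as a minor one. The synopsis collection period is shorter than the stated 30-day analysis window and conflicts with the labs scheduled at post-treatment Week 12. The shortfall against the analysis window is 2 days, 1.8% or 1.0% of the period from first dose, and on its own would hardly move an SAE rate.

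The more consequential gap is about 54 days long: SAEs that begin after day 30 are assessed but have no stated rule for entry or reporting, and the entry rules in 7.1 and 7.2 would generally keep out any SAE that begins after the last dose. This rests on reading those two rules as written.

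Completion of therapy and SVR12 are unaffected. How many events are concerned cannot be known from the documents; the admission counts above rest on assumed rates and full follow-up and show scale only.

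**What to change.** Reconcile the synopsis, 5.2.7, Appendix 1, 7.1, 7.2 and 8.6 in one edit:
- Enter SAEs and deaths at least through day 30 after the last dose, and preferably through the existing post-treatment Week 12 visit.
- Amend 7.1 and 7.2, and the scope of the AE page of the CRF, so that SAEs are entered whether or not they lead to discontinuation. Without this, changing the synopsis period has little effect.
- Extend the synopsis period for labs so that the scheduled Week 12 samples fall inside it.
- Keep last dose + 30 days for treatment-emergent events, and state in 8.6 that the SAE rate uses that window.
- List SAEs and deaths with onset from day 31 to the Week 12 visit separately, by cohort.

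If collection to Week 12 is not wanted, aligning the synopsis and the entry rules with day 30, bringing the Week 12 labs inside the collection period, and stating that later SAEs are not entered would remove the contradiction, at the price of leaving late events unreported.

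The cost is slightly more data entry, the change to the CRF scope, and one descriptive listing. No visit or procedure is added. A few more events would be reported, probably mostly from the underlying heart or lung disease; the separate listing keeps them out of the treatment-emergent rate.

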8.6.1. Adverse Events

Clinical and laboratory adverse events will be summarized on the basis of the date of onset for the event. A treatment-emergent adverse event will be defined as any adverse event that begins on or after the date of first dose of medicinal product up to the date of last dose of medicinal product plus 30 days.

8.6.2. Laboratory Evaluations

Selected laboratory data will be summarized (n, mean, SD, median, Q1, Q3, minimum, and maximum) and study visit along with corresponding change from Baseline/Day 1. These laboratory data to be analyzed are:

Hematology: Hemoglobin (Hb), Platelet count, White blood cell count (WBC)

Coagulation: INR, Prothrombin time (PT)

Chemistry: Alanine aminotransferase (ALT/SGPT), Aspartate aminotransferase (AST/SGOT), Albumin, Alkaline phosphatase, Serum Creatinine, Total Bilirubin (Direct Bilirubin as reflex if total is elevated)

Virologic Tests: HCV RNA; HCV genotype and subtype; HIV

9. INVESTIGATOR & SPONSOR RESPONSIBILITIES

9.1. Investigator Responsibilities

9.1.1. Good Clinical Practice

The investigator will ensure that this study is conducted in accordance with the principles of the "Declaration of Helsinki" as expressed in the International Conference on Harmonisation (ICH) guidelines (ICH E6), or with the laws and regulations of the country in which the research is conducted, whichever affords the greater protection to the study subject.

9.1.2. Institutional Review Board (IRB)

This protocol will be submitted by the investigator to an IRB (for studies conducted in the United States. Approval from the IRB must be obtained **before** starting the study and should be documented in a letter to the investigator specifying the protocol number, protocol version, protocol date, documents reviewed, and date on which the committee met and granted the approval. A copy of the IRB-approved Informed Consent Form (ICF) should be included with the approval documents. Any modifications made to the protocol after receipt of IRB approval must also be submitted to the IRB, for approval before implementation.

9.1.3. Informed Consent

The investigator is responsible for obtaining written informed consent from each individual participating in this study after adequate explanation of the aims, methods, objectives, and potential hazards of the study and before undertaking any study-related procedures. The investigator must utilize an IRB- approved consent form for documenting written informed consent. Each informed consent will be appropriately signed and dated by the subject or the subject's legally authorized representative and the person obtaining consent.

9.1.4. Confidentiality

The investigator must assure that subjects' anonymity will be strictly maintained and that their identities are not disclosed to unauthorized parties. Only an identification code (i.e. not names, initials, or date of birth) should be recorded on any form or biological sample submitted to the Sponsor, IRB, or laboratory. The investigator agrees that all information received from the sponsor, including but not limited to the protocol, CRFs, and any other study information, remain the sole and exclusive property of the sponsor during the conduct of the study and thereafter. This information is not to be disclosed to any third party (except employees or agents directly involved in the conduct of the study or as required by law) without prior written consent from the sponsor. The investigator further agrees to take all reasonable precautions to prevent the disclosure by any employee or agent of the study site to any third party or otherwise into the public domain.

9.1.5. Drug Accountability

The investigator is responsible for ensuring accountability of all used and unused study drug. This includes acknowledgment of receipt of each shipment of study product (quantity and condition), subject dispensing records, and returned or destroyed study product. Dispensing

records will document quantities received and quantities dispensed to subjects, including lot number, date dispensed, subject identifier number, subject initials, and the initials of the person dispensing the medication. Documentation will be maintained by the site; no data will be entered into the database.

9.1.6. Study Files and Retention of Records

The investigator must maintain adequate and accurate records to enable the conduct of the study.

The investigator's study file will contain the protocol/amendments, IRB approval, approved ICF, and drug records, at a minimum, source records to be documented in the medical record by the investigator are listed below:

- subject identification by study code;
- documentation that subject meets eligibility criteria, i.e., history, physical examination, and confirmation of diagnosis (to support inclusion and exclusion criteria);
- participation in trial (including trial number);
- date of informed consent;
- dates of all visits:
- documentation that protocol specific procedures were performed;
- results of efficacy parameters, as required by the protocol;
- start and end date (including dose regimen) of medication record of all adverse events and other safety parameters (start and end date, and preferably including causality and intensity);
- concomitant medication (including start and end date, dose if relevant; dose changes should be motivated);
- date of trial completion and reason for early discontinuation, if applicable.

